15.2 Study Design

The study will follow a two-arm, double-blind, placebo-controlled approach. Allocation will be 1:1 between the two groups. Study subjects, treating physicians, medical assistants, and other members in the research team who conduct subject contact and/or data analysis will remain blinded throughout the study period.

15.3 Randomization

To better ensure equivalent group sizes in the event of unenrollment or loss-to-follow-up, a block randomization scheme will be followed with block size of $n=8$. The following steps will be adhered to when enrolling a subject into one of the two study arms:

1. Eight tokens, numbered 1-8, will be held in a jar stored in the study manager's office within TSC and SPRI.
2. Upon enrollment, a token will be drawn from the jar, and not replaced back into the jar.
3. The Block Number and Within-Block Number will be recorded by the study team on a blinded version of the Enrollment/Randomization log.
4. The Block Number and Within-Block Number will be disclosed to the Vail Health Hospital Pharmacy who will arrange the proper medication and record the subject onto an unblinded version of the Enrollment/Randomization log.

-
- When final token is taken from jar, enrollment within that block is complete, and all 8 tokens will be placed back in the jar in preparation for the next subject and the new block.

Figure 15.3 Portion of the randomization/enrollment log demonstrating group allocation for subjects enrolled into block #1.

Block Number	Within-Block Number	Group (Randomization not finalized, for illustration only)	Subject ID
		Patient	
		Enrollment	
		Date	
1	1	Fisetin	1
	2	Placebo	2
	3	Placebo	3
	4	Fisetin	4
	5	Placebo	5
	6	Fisetin	6
	7	Fisetin	7
	8	Placebo	8

15.4 General Data Handling, Analysis, and Reporting Strategy

Intent-to-treat analysis will be performed.

Baseline covariates will be summarized and reported in a table, stratified by group. This is a randomized trial, thus the expected population group differences with respect to baseline covariates are zero by definition. For this reason, no statistical comparisons will be performed to test for differences in baseline covariates between groups.

Whenever applicable, assessment of endpoints that are measured at serial time points will be analyzed using methods that account for this repeated measure structure. Listwise deletion in response to missing data points and categorization/dichotomization of continuous measurements will be avoided to every extent possible.

Summary statistics will be reported as group medians with quartiles or extrema. Meanwhile estimates calculated for statistical inference will be reported with $(1-\alpha)\%$ confidence intervals. Model fit and satisfactorily meeting model assumptions will be assessed for all multivariable regression and linear mixed-effects models using residual analysis.

The Statistical Computing Language R will be used to produce all analyses and plots.

15.5 Endpoints

15.5.1 Primary Endpoint

The safety of FIS administration is the primary endpoint of this study. All adverse events will be compared by category of description incidence, relatedness to treatment, severity, duration and expectedness. The occurrence of non-serious and serious and unexpected adverse events will be compared between treatment groups. Bivariate analysis will be performed between group and each safety variable of interest independently. When comparing the two treatment groups, dichotomous (yes/no) endpoints will be assessed for association using Fisher's exact test. Adverse events and symptoms that may occur multiple times in a single subject will be analyzed as count variables, and group differences will be assessed using simple Poisson regression or simple negative binomial regression.

This is a small Phase I/II trial in which to assess safety, thus we will report all safety data thoroughly and aim to liberally identify potential side-effects and risks that may warrant close study in future, larger trials. No adjustments will be made for multiple comparisons in this set of safety endpoints.

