15.6 Statistical Power and Sample Size

Anticipated effect sizes for the group difference with respect to MRI-assessed cartilage quality were derived from the literature, however a paucity of literature was found in the knee OA literature when comparing various grades of advanced osteoarthritis. As a simplifying assumption, we derived an anticipated effect size for clinically meaningful change in T1rho values from a recent meta-analysis (MacKay, et al, 2018, J Osteoarthritis and Cartilage) that reported the standardized mean difference (SMD) between mild OA and healthy controls.

We aim to power this study to detect an effect size between the FIS and placebo treatment groups that is equal to the meta-analyzed effect size described above (SDM=0.73). The statistical method for this unadjusted, independent groups comparison of means, and the significance level will be set at $\alpha=0.05$. Assuming 2-tailed testing and requiring 80% statistical power, 30 patients per group are sufficient to detect the effect size of interest. Anticipating a 20% drop-out or incomplete follow-up rate, we aim to enroll no more than 100 total OA patients (30 per groups, and 6 per group to account for 20% drop out). Power calculations were performed using G*Power (version 3.1; Universität Düsseldorf).

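### Section 15.5.1 could serve its own aim of liberal harm detection better, at small cost, by replacing Fisher's exact test with Boschloo's test built on Fisher's two-sided p-value

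*Combined protocol and SAP*

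**What the plan says.** Section 15.5.1 makes safety the primary endpoint and examines each safety variable against treatment group separately. For the comparison of the two groups, "dichotomous (yes/no) endpoints will be assessed for association using" Fisher's exact test. Events that can recur within a subject are treated as counts, with Poisson or negative binomial regression.

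The section presents the trial as small and early, with the intention to "aim to liberally identify potential side-effects and risks that may warrant close study in future, larger trials". In line with that, "No adjustments will be made for multiple comparisons in this set of safety endpoints".

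It gives no significance level or sidedness for these tests. Both appear only in section 15.6, for the MRI-based sample size: alpha 0.05, and "Assuming 2-tailed testing and requiring 80% statistical power". Nothing is said about the error rate or power of the safety comparisons.

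The number per arm is not settled. Section 6.0 gives 36 per arm, and section 15.6 builds up to 36 per arm. The synopsis gives 100 in total, and sections 7.5.1 and 15.6 give no more than 100.

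**The concern.** Fisher's test conditions on the total number of subjects with the event. In small samples few tables share a given total, so the attainable p-values are widely spaced and the test usually operates well below its nominal level. The shortfall is greatest for uncommon events, which is where an early safety comparison most needs sensitivity.

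A plan that accepts false alarms in order to notice harms has therefore chosen a test that leaves part of its error allowance unused. What is at stake is power to flag a difference in the occurrence of a given adverse event.

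**Working it through.** **Inputs.** Arms of 36 (sections 6.0 and 15.6) or 50 (half of the synopsis total of 100), allocated 1:1 in blocks of 8 (15.3). Two-sided 0.05 is borrowed from 15.6 as an assumption. The documents give no adverse event rates, so all rates below are illustrative.

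**The plan's own figure.** Section 15.6 needs 30 per group for a standardized difference of 0.73: n = 2(1.960 + 0.842)² / 0.73² = 15.70 / 0.533 = 29.5, so 30. Then 30 × 1.2 = 36. This reproduces, but it concerns T1rho and says nothing about safety.

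**Fisher.** For x of n1 and y of n2 subjects with the event, and m = x + y, the conditional probability of k events in arm 1 is C(n1,k)·C(n2,m−k)/C(n1+n2,m). The two-sided p-value sums these over all k that are no more probable than the observed table. The true error at a common rate π is the sum of Bin(x; n1, π)·Bin(y; n2, π) over all tables with p ≤ 0.05. The maximum is taken over π.

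**Boschloo.** Take the largest cut-off c on Fisher's two-sided p-value for which that maximum is still at most 0.05. Fisher's own maximum is below 0.05, so c is at least 0.05 and every Fisher rejection is kept. At 36 v 36, c = 0.0847, which adds 56 tables.

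**Maximum true error by full enumeration**

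| Arms | Fisher | Boschloo |
|---|---|---|
| 36 v 36 | 2.79% | 4.94% |
| 36 v 35 | 3.69% | 4.98% |
| 37 v 35 | 3.90% | 4.84% |
| 38 v 34 | 3.93% | 4.93% |
| 50 v 50 | 3.52% | 4.87% |
| 50 v 49 | 4.39% | 4.94% |

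At 36 v 36 and a common event rate of 5%, 10% or 20%, Fisher's true error is 0.3%, 1.4% or 2.6%. Boschloo's is 1.2%, 3.4% or 4.8%.

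**One table by hand, 36 per arm.** For 5 v 0, Fisher p = 2·C(36,5)/C(72,5) = 2 × 376,992 / 13,991,544 = 0.054, not significant. For 6 v 0, p = 2 × 1,947,792 / 156,238,908 = 0.025. So Fisher needs six cases against none. Boschloo needs five (p = 0.033 for 5 v 0).

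**Power, Fisher to Boschloo**

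| Rates | 36 v 36 | 36 v 35 | 50 v 50 |
|---|---|---|---|
| 15% v 0% | 46% to 65% | 46% to 65% | 78% to 89% |
| 25% v 5% | 57% to 69% | 58% to 63% | 75% to 80% |
| 30% v 10% | 47% to 58% | 49% to 51% | 64% to 70% |

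The first row can be checked directly. With no placebo cases, power is P(X ≥ 6) for Fisher and P(X ≥ 5) for Boschloo, with X ~ Bin(36, 0.15) or Bin(50, 0.15).

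**Which arm sizes are realistic?** 72 = 9 × 8, so 72 randomized subjects fill nine blocks and give exactly 36 v 36. But 100 = 12 × 8 + 4, so at 100 the last block is half used and the arms could differ by up to four.

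**The case against.** Several stronger readings are tempting, and the documents do not support them.

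- *The plan is wrong or contradicts itself.* A reader might infer this from the word liberally. But Fisher's test is valid and conventional, and 15.5.1 pursues its aim in other ways: full reporting of safety data and no multiplicity adjustment.
- *The test's true error in this trial is at most 2.8%.* That holds only for exactly 36 v 36. The other arm sizes compatible with the documents give 3.5% to 4.4%. The gain for more common events also depends heavily on balance: for 30% v 10%, losing one subject from one arm cuts it from about 10 points to 2.
- *The change costs nothing.* At a 10% event rate and 36 per arm, false positives per test rise from 1.4% to 3.4%. Over an assumed 20 independent tests, the chance of at least one false signal goes from 1 − (1 − 0.0138)^20 = 24% to 1 − (1 − 0.0338)^20 = 50%. The plan appears willing to make that trade, but it is a trade.
- *Boschloo is never less powerful.* This is true with Fisher's two-sided p-value as the statistic. It is not true of versions that double a one-sided p-value: for 2/36 v 8/35, Fisher gives 0.046 and the doubled version 0.057. At 38 v 34 the doubled version has less power than Fisher for 25% v 5% (59.9% against 63.9%).
- *This is the trial's only safety comparison.* Count regressions are also planned, as are comparisons by relatedness, severity, duration and expectedness.

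What remains is a gain that is large for harms absent on placebo, in every arm size tried, and modest to moderate elsewhere.

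**Conclusion.** This is a worthwhile, low-cost improvement and not a defect. Fisher's test leaves part of a 5% error allowance unused, most of all for uncommon events, while the section asks for liberal detection. Boschloo's test on Fisher's two-sided p-value recovers much of that allowance without exceeding 5% in any configuration computed. The gain is 11 to 19 percentage points of power for 15% v 0%, and as little as 2 points for 30% v 10% in slightly unequal arms.

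The result rests on two-sided alpha 0.05, which 15.5.1 does not set, on assumed event rates, and on arm sizes that the documents leave open.

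**What to change.** In section 15.5.1, before unblinding:

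1. Replace Fisher's test with Boschloo's unconditional exact test for dichotomous safety variables.
2. Specify that the two-sided test statistic is Fisher's two-sided p-value and not a doubled one-sided p-value. Confirm that the chosen R function uses this definition.
3. State the alpha and sidedness that apply to the safety tests.
4. Report the risk difference with a confidence interval and name the interval method. Section 15.4 already promises intervals for inferential estimates but does not name this measure.

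Separately, reconcile 36 per arm with the total of 100, because the operating characteristics depend on it.

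The cost is a few lines of text and a different R function, with no added subjects or procedures. The test is less familiar, and the report should acknowledge the higher false-positive rate per test across unadjusted comparisons.

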15.5.2 Secondary Endpoints

15.5.2.1 Imaging Assessment of OA

Quantitative MRI will be performed at baseline and at 6 months and 12 months after initiation of medication. T2 and T1rho relaxometry will be performed. Linear mixed-effects modeling with random intercepts will be used to appropriately match the repeated measures design. A group-by-time interaction will be modeled to investigate both early improvement in tissue quality and maintenance of such an effect to 12 months as well.

Secondarily, multivariable modeling techniques such as support vector machines (SVM) and/or principal components analysis (PCA) will be pursued to characterize the SASP response profile that distinguishes the FIS and placebo groups.

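### The stated 80% power belongs to an unadjusted T1rho comparison, not to the planned group-by-time contrast, whose power depends on an unstated between-visit correlation; a common baseline mean gains precision at no cost in data

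*Combined protocol and SAP*

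**What the plan says.** Section 15.6 is the only power calculation in the document, and it concerns MRI: "we derived an anticipated effect size for clinically meaningful change in T1rho values from a recent meta-analysis". The target is a difference "equal to the meta-analyzed effect size described above (SDM=0.73"), a figure that compares mild OA with healthy controls. The test is described as "The statistical method for this unadjusted, independent groups comparison of means", two-sided at alpha 0.05, and the result is: "Assuming 2-tailed testing and requiring 80% statistical power, 30 patients per group are sufficient to detect the effect size of interest". The section names no visit.

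Section 15.5.2.1 schedules MRI at baseline, 6 and 12 months, with T2 and T1rho relaxometry, and analyses them by a linear mixed model with random intercepts: "A group-by-time interaction will be modeled to investigate both early improvement in tissue quality", and also whether such an effect is maintained to 12 months. It does not say whether the arms may differ in mean at baseline, which coefficient is the test, or which measure and visit carry the 0.05.

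Two other sections bear on this. Section 15.4 says that randomization makes the expected baseline differences zero. Section 15.5.2.3 uses ANCOVA with the baseline value as covariate for the patient-reported outcomes.

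**The concern.** The power statement and the analysis describe different estimators. A two-group comparison at follow-up ignores baseline. A group-by-time contrast with separate baseline means subtracts it in full. Full subtraction helps when repeat scans on the same knee correlate strongly and hurts when they do not, because the noise of the baseline scan is added to that of the follow-up scan.

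If the interaction is the test, the trial's only powered outcome could have clearly less than 80% power, and the documents give no correlation from which to judge. The loss would also be avoidable: in a randomized trial baseline can be used in a way that never does worse than ignoring it, apart from a negligible loss of degrees of freedom.

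**Working it through.** **Inputs.** From 15.6: standardized difference 0.73, two-sided alpha 0.05, 30 evaluable per group, 20% dropout. From 15.2: 1:1 allocation. From 15.5.2.1: visits at baseline, 6 and 12 months, random intercept. Assumed: rho, the correlation between any two visits, is not given and is taken from 0.3 to 0.7. It is constant across visits, as a random intercept implies. Data are complete for the evaluable patients. The 0.73 is in units of the between-person SD, since it comes from a comparison of two groups of people.

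**Step 1: the plan's own figure.** The noncentrality is 0.73 × sqrt(30/2) = 2.83. The noncentral t with 58 degrees of freedom gives 79.4% power (80.7% by the normal approximation). The stated 30 per group is reproduced to within rounding.

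**Step 2: the interaction contrast with separate baseline means.** It equals the between-arm difference in (follow-up minus baseline). With unit variance at each visit, the variance of a change is 1 + 1 - 2rho = 2(1-rho). Power follows from noncentrality 2.83 / sqrt(2(1-rho)).

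**Step 3: the same model with a common baseline mean, or baseline as covariate.** The follow-up difference then has residual variance 1 - rho². Power follows from noncentrality 2.83 / sqrt(1-rho²).

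Power at 30 per group:

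| rho | variance ratio, separate baselines | power | variance ratio, common baseline | power |
|---|---|---|---|---|
| 0.3 | 1.40 | 65% | 0.91 | 83% |
| 0.4 | 1.20 | 72% | 0.84 | 86% |
| 0.5 | 1.00 | 79% | 0.75 | 89% |
| 0.7 | 0.60 | 95% | 0.51 | 97% |

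A generalized least squares calculation for three visits with equal correlations returns the same variance ratios at rho 0.3, 0.5 and 0.7.

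**Step 4: comparison that does not need rho.** The ratio of the two variances is (1-rho²) / (2(1-rho)) = (1+rho)/2, which is below 1 for every rho below 1. The common-baseline model is therefore always more precise than the interaction contrast. Because 1-rho² is at most 1, it is also never less precise than the unadjusted comparison.

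**Step 5: other sample sizes and contrasts.** The synopsis gives 100 subjects in total. With 50 per arm and 20% dropout, 40 remain per arm. The interaction contrast then has 78% power at rho 0.3, 84% at 0.4 and 90% at 0.5, and reaches 80% at rho of about 0.34. The common-baseline model gives 92% at rho 0.3. If instead the contrast is the mean of both follow-up visits minus baseline, at 30 per group and with a difference of 0.73 at both visits, the variance ratio is 1.5(1-rho) and 80% is again reached at about 0.34.

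**Step 6: another contrast in the same model.** The between-arm difference at a follow-up visit, read from the model with separate baselines, has a variance ratio of exactly 1.0 in the least squares calculation. It keeps the 79.4% of Step 1.

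**The case against.** The strongest reply is that the plan is underspecified here, not wrong. Section 15.5.2.1 says only that the interaction will be modeled. It does not say that each arm has its own baseline mean or that the interaction coefficient is the test. Section 15.4 is compatible with a common baseline mean, and the ANCOVA in 15.5.2.3 shows that the authors know how to adjust for baseline. This stands in part: separate baselines are the usual meaning of a group-by-time model with baseline among the visits, but they are an inference.

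A reader might infer that the powered outcome has no contrast in the analysis with the stated power. That goes too far. The model also yields the between-arm difference at a visit, with the sized variance (Step 6). What is missing is a statement that this is the intended test.

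A reader might also infer that the MRI analysis is underpowered, or that 0.5 is a general threshold. The documents do not support either. They give no correlation, and above 0.5 the interaction contrast does better than the sized comparison. One scanner and a sample spanning Kellgren-Lawrence grades II to IV could favor a higher correlation, though neither proves it. The 0.5 applies only to a visit-specific contrast at 30 evaluable per group.

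Finally, two measures at two visits might suggest an error rate of 1 - 0.95⁴ = 18.5%. That is an upper figure for picking the best of four independent tests. The plan makes no such claim, and the 6- and 12-month contrasts share a baseline scan and so are correlated.

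None of this removes the case for the change, since Step 4 holds whatever the correlation.

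**Conclusion.** The mismatch between 15.6 and 15.5.2.1 is real. On the usual reading, the visit-specific interaction contrast at 30 evaluable per group has about 65% to 95% power as rho runs from 0.3 to 0.7. It falls below the sized comparison when rho is under 0.5 and above it otherwise; with 40 evaluable per group it reaches 80% at about 0.34. The shortfall is thus conditional on an unknown correlation, on separate baseline means, and on the interaction being the test.

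The improvement needs no value of rho. A common baseline mean, or baseline as covariate, beats the interaction contrast at every rho below 1; in the range shown it gives 83% to 97%. These figures assume equal correlations between visits and complete data. Since MRI is secondary and safety is primary, this is a precision gain that should be taken and not a threat to the trial's main conclusion.

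**What to change.** In 15.5.2.1, keep the mixed model but constrain the two arms to one common baseline mean, that is, allow group differences only at 6 and 12 months. Equivalently for this purpose, use baseline as a covariate with 6 and 12 months as the outcomes. Define the treatment effect as the between-arm difference at a visit.

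In 15.6, state that the power and the 0.05 refer to the T1rho between-arm difference at one named follow-up visit from that model, with T2 and the other visit supportive. The constraint alone does not choose the visit or the measure, so both edits are needed.

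The cost is one model term and a few sentences. No patient, visit or scan is added: the baseline MRI is already listed at Visit 2, where the first dose is taken. Because allocation is randomized and blinded, the common baseline mean remains justified even where randomization is done at screening, before the baseline scan.

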15.5.2.2 Kinematic, Strength and Functional Performance Testing

Measurements from the timed-up-and-go test (TUG), 4-meter walk test (4mW), 6-minute walk test (6MW), time to descend 9-12 stairs test (SCT), video motion capture of lower-extremity kinematics, and isokinetic muscle test using the HUMAC NORM system will be assessed as continuous variables. Previous testing has identified these measurements follow a relatively Gaussian distribution, so parametric comparison of means (Welch's t-test) is planned between treatment groups.

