15.5.2.3 Pain and PRO Assessment

The hypothesis in this study is that FIS will induce a systemic anti-inflammatory and senolytic effect, thereby reducing pain and improving self-reported function and quality of life compared to the placebo group. Early subjective assessment (every 3 days for 6 weeks following the first dose of study medication and once weekly for the following 6 weeks) will be limited to a short augmented numerical rating scale questionnaire. Linear mixed-effect random-intercepts modeling will be used to characterize the trend in self-reported pain over 3 months, and to test whether treatment group is a significant predictor of pain reduction.

The IKDC, WOMAC, Tegner activity scale and Lysholm PRO measures will be administered at 2 weeks after the last dose of study medication and 6, 12, and 18 months following initiation of medication. For each time point, ANCOVA will be used with the subject's baseline PROM value used as a covariate. Among the 4 postoperative time-points for assessing these validated PROMs, the Holm-Bonferroni method will be used to control the family-wise type-1 error rate to 0.05 within each PROM scale tested. No multiplicity adjustments will be made across different PROMs, which are commonly highly intercorrelated.

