15.5.2.4 Conversion to Secondary Interventions

In important endpoint for subjects enrolled in this study will be conversion to alternative treatments. The protocol allows for a single intra-articular corticosteroid injection into the knee to manage knee pain without necessitating removal of the subject from the study. However, if a study subjects elects to convert to a regenerative medicine treatment (e.g. platelet rich plasma or bone marrow aspirate concentrate) or a surgical intervention (e.g. microfracture or total joint replacement), they will be removed from the study. Cox proportional hazards regression will be performed to compare the hazard rate of conversion to each of these two treatment categories between treatment groups.

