15.7 Missing Data

Whenever possible, statistical methods such as linear mixed-effects modeling which naturally handle missing data will be utilized. Missing data will be investigated carefully by the biostatistician, the study manager and the clinical staff to assess its probable cause, and whether missing not at random (MNAR, missingness dependent on outcome), missing at random (MAR, missingness not dependent

on outcome but can be fully accounted for by other non-missing covariates) or missing completely at random (MCAR, missingness independent of both observed variables and unobserved parameters of interest) is most likely.

If any missing data patterns are determined to be MNAR, this observance will be reported narratively in the final report(s) and publication(s), and no imputation methods will be pursued. Little's test will be used to assess whether missing values are missing completely at random (MCAR). For methods that require complete data or listwise deletion (e.g. PCA), and where missing data is determined to be reasonably missing at random (MAR or MCAR), multiple imputation using predictive mean matching will be employed.

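### Section 15.5.2.2 names no baseline adjustment, outcome scale or visit for the kinematic, strength and functional measures; ANCOVA on the baseline already collected would usually be more precise and would settle the scale.

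*Combined protocol and SAP*

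**What the plan says.** Sections 11.7, 11.8 and 11.9 schedule functional performance, video-motion kinematics and isokinetic strength at Visits 2, 5 and 6. That gives one pre-dose value and follow-up values at 6 and 12 months.

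Section 15.5.2.2 treats these measures as continuous. It states "Previous testing has identified these measurements follow a relatively Gaussian distribution", "so parametric comparison of means (Welch's t-test) is planned between treatment groups". It mentions no covariate, no visit, and neither value nor change.

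Other parts of the statistical section lean a different way:

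- Section 15.4: "Whenever applicable, assessment of endpoints that are measured at serial time points will be analyzed using methods that account for this repeated measure structure".
- Section 15.7: "Whenever possible, statistical methods such as linear mixed-effects modeling which naturally handle missing data will be utilized". For methods that need complete data, and where data are judged missing at random, "multiple imputation using predictive mean matching will be employed".
- Section 15.5.2.3 analyses the IKDC, WOMAC, Tegner and Lysholm scores by ANCOVA at each time point, with the "baseline PROM value used as a covariate".

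**The concern.** Each measure has a baseline and two follow-up values, so the section allows at least four tests per measure: value or change, at 6 or 12 months. These tests differ in precision and can give different answers on the same data.

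The reason given for the Welch test, approximate normality, supports a parametric method. It is not a reason to leave out a baseline already in hand. The same plan uses that baseline for the patient-reported outcomes.

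At stake is the chance of seeing a real functional effect in a small trial, and whether a reader can tell which comparison was intended.

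**Working it through.** **Inputs.** From Section 15.6: 30 evaluable patients per group, two-sided α = 0.05, and a standardised mean difference (SMD) of 0.73. That SMD was derived for T1rho, not for functional measures. The plan gives no effect size or correlation for the measures in Section 15.5.2.2. Two inputs are therefore assumptions: a second SMD of 0.4, and a correlation ρ between baseline and follow-up of 0 to 0.9. I also assume normal data, equal SDs at baseline and follow-up, and the same ρ in both arms.

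**The plan's own figure.** n per group = 2 × (1.960 + 0.842)² / 0.73² = 29.5, rounded up to 30. Exact noncentral-t power is 79.4% at 30 per group and 80.7% at 31, so the stated 30 reproduces to within rounding.

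**Variance of the group difference, relative to a t-test on follow-up values.**

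- Change from baseline: 2(1 − ρ).
- ANCOVA: (1 − ρ²) × (1 + 1/(N − 4)). With N = 60 the second factor is 57/56 = 1.018. The error degrees of freedom are 57, against 58 for an equal-variance t-test.

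**Power.** With variance ratio f, the noncentrality is SMD × √(30/2) / √f. At SMD 0.73 and ρ = 0.5, ANCOVA has f = 0.75 × 1.018 = 0.763 and noncentrality 0.73 × 3.873 / 0.874 = 3.24, giving 88.9% power. All cases, in the order values / changes / ANCOVA:

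| ρ | f, change | f, ANCOVA | Power, SMD 0.4 | Power, SMD 0.73 |
|---|---|---|---|---|
| 0.3 | 1.40 | 0.926 | 33 / 25 / 35% | 79 / 65 / 82% |
| 0.5 | 1.00 | 0.763 | 33 / 33 / 41% | 79 / 79 / 89% |
| 0.7 | 0.60 | 0.519 | 33 / 50 / 56% | 79 / 95 / 97% |
| 0.8 | 0.40 | 0.366 | 33 / 67 / 71% | 79 / 99 / >99% |
| 0.9 | 0.20 | 0.193 | 33 / 93 / 93% | 79 / >99 / >99% |

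At SMD 0.4, ANCOVA gains about 10 points over changes at ρ = 0.3 and under 1 point at ρ = 0.9. Over values, it gains about 2 points at ρ = 0.3 and 60 at ρ = 0.9. At SMD 0.73 the unstated scale alone moves power from 79% to 65% at ρ = 0.3, and from 79% to 95% at ρ = 0.7.

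**Where ANCOVA loses.** Against values, break-even is (1 − ρ²) × 57/56 = 1, so ρ = √(1/57) = 0.13. At ρ = 0 power falls from 79.4% to 78.7% (SMD 0.73) or from 33.2% to 32.7% (SMD 0.4). Against changes, break-even is (1 + ρ) × 57/56 = 2, so ρ = 0.965; the loss beyond that is negligible.

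**Validity.** In simulation (6,000 trials per setting, 30 per arm, ρ from 0 to 0.7), type I error was 4.7 to 5.3% for all three methods.

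**Value or change.** With baseline X in the model, replacing outcome Y by Y − X lowers only the coefficient of X, by 1. The group difference and its standard error do not change.

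**The case against.** Several stronger readings are tempting, and the documents do not support them.

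- A reader might infer that the plan ignores the baseline. It may not: a Welch test on changes uses it, and Section 8.2.2 words these endpoints as improvement, which points towards change. What can be said is that no adjustment is named and the scale is undefined.
- A reader might infer that the plan contradicts its own rules. The preferences in Sections 15.4 and 15.7 are qualified by applicability and possibility. This is a departure from a stated preference. The mixed model for MRI is a different method for a different endpoint.
- A reader might infer that drop-out biases the t-test and that ANCOVA cures it. Section 15.6 budgets for losses ("Anticipating a 20% drop-out or incomplete follow-up rate"), and Section 15.5.2.4 says of subjects converting to regenerative or surgical treatment that "they will be removed from the study". But the mechanism is unknown, Section 15.7 provides imputation where it is judged suitable, and ANCOVA at one visit also uses only subjects seen at that visit. If removal depends on unobserved outcomes, none of these methods removes the bias.
- A reader might infer freedom to pick the favourable test. Section 15.8 defers inference to study completion and masks the groups as A and B. That limits selective choice, although it settles neither scale nor visit.

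Two objections stand in full. Plain ANCOVA gives up Welch's allowance for unequal variances, so the replacement must restore it. The gain also depends on a correlation that the documents do not give. A repeated-measures model is defensible but is not required by this argument.

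**Conclusion.** The point holds as a matter of precision and pre-specification for secondary endpoints. Section 15.5.2.2 leaves scale and visit open and names no use of a baseline that the trial collects. The primary safety endpoint is untouched, and the t-test is valid with complete data or data missing completely at random.

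The gain ranges from negligible to large. At an SMD of 0.73, ANCOVA has 89% power at ρ = 0.5 and 97% at ρ = 0.7, against 79% for a t-test on values. At lower correlations the advantage over values is small; at high correlations the advantage over changes is small. ANCOVA is close to the better of the two throughout, which matters because ρ is unknown. The size rests on the assumed effects and correlations, equal SDs and 30 completers per arm. The revision is worth making because it is cheap and the plan already uses the method.

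**What to change.** In Section 15.5.2.2, replace the Welch test with ANCOVA of the 6-month and 12-month values on the pre-dose baseline (Visit 2, or Visit 1 where the test was done then), as Section 15.5.2.3 does for the patient-reported outcomes. Use heteroscedasticity-robust standard errors, in a form suited to small samples, to keep Welch's protection against unequal variances. Report the group difference and its confidence interval at both visits. The choice between value and change then no longer affects the estimate.

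Optional alternative: one repeated-measures model per measure with group, baseline, visit, group-by-visit and baseline-by-visit, allowing group-specific variances if residuals call for them. It also uses subjects with a missing visit, in line with the preferences in Sections 15.4 and 15.7.

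The cost is SAP wording. No new data are needed, and Section 15.4 already requires residual checks for such models. The statistical price is one degree of freedom, and under 1 power point relative to a t-test on values if the baseline correlation is below about 0.13.
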